
[figure not shown]
Specific Aims

- Aim 1: To investigate the efficacy of active FES vs. passive FES, as measured by changes in behavioral measures. Hypothesis: We hypothesize that improvements in motor function will be significantly greater using the active FES therapy than the passive FES therapy.
- Aim 2: To investigate the relationship between brain functional activation patterns and behavior changes induced by active vs. passive FES intervention. Hypothesis: We hypothesize that changes induced by active FES (as measured by brain fMRI and EEG measures) will show greater adaptive brain reorganization changes (i.e. brain changes that correlate with improved outcomes) than that induced by the passive FES.
- Aim 3: To investigate the relationship between brain white matter integrity and behavior changes induced by active vs. passive FES intervention. Hypothesis: We hypothesize that changes induced by active FES (as measured by brain DTI measures) will show greater adaptive brain reorganization changes (i.e. brain changes that correlate with improved outcomes) than that induced by the passive FES.

Research Design and Methods

This is a prospective, longitudinal study in which stroke patients with upper-limb hemiparesis will be adaptively randomized to two groups: **Active FES (aka the experimental group)**, and **Passive FES aka (the control group)**. Adaptive randomization in our study will be done based on age and severity of UE impairment (see Figure 1).

Participants: 144 patients will be enrolled in the study following inclusion/exclusion criteria below:

Inclusion criteria: ages 50-85 years; new-onset ischemic stroke 12 months prior – chronic time frame; right hand dominant – affected arm; mild to moderate unilateral upper extremity(UE) impairment (Action Research Arm Test; ARAT score > 35) or severe unilateral upper extremity(UE) impairment (ARAT score <= 35); no upper extremity injury or conditions that limited use prior to the stroke; pre-stroke independence with a Modified Rankin Score of 0 or 1, and the ability to provide informed consent on their own behalf.

Exclusion criteria: Inability to competently participate in study procedures, Concurrent upper extremity therapy, other neurological (e.g., AD) or psychiatric disorders.

Note, participants with contraindications to MRI will continue to be eligible for this research and will be asked to participate in both the computer training and the behavioral assessments.

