Randomization: Patients will be adaptively randomized, based on age (50-64 years and 65-85 years), and severity (severe – ARAT > 35, non-severe – ARAT <= 35), to two groups – the active FES group receiving intervention with the active FES (n = 72) and the passive FES group receiving FES only intervention (n=72). Advancing age has a major negative impact on stroke morbidity, mortality; older adults (> 65 years) have increased chance of dying after stroke and being discharged to the skilled nursing facility if they survive, therefore age 65 will be used as a cut-off. There is some evidence that patients with ARAT scores above or below 35 show clear differences in recovery [41], therefore ARAT of 35 will be used as a cutoff.

Subject identification and Recruitment

Subject Identification:

- a) Through referrals by the Stroke Neurology team or other UWHC or UW Rehab hospital or The American Center (TAC) clinicians involved in patient care, in the in-patient or outpatient setting.
- b) Clinicians involved in the care of patients may send recruitment letters to eligible patients and ascertain their interest in study participation.
- c) A stroke service patient log maintained by the UW-Madison Stroke Neurology section UWHC or UW Rehab hospital or TAC clinicians will be used to identify patients.
- d) By posting recruitment flyers in community newsletter, at different locations such as the UWHC, the School of Medicine, UW libraries, the University Station Clinic, St. Mary's hospital, Meriter hospital, as well as UW out-patient clinics and rehab centers outside the Madison area, Madison public libraries, stroke support and other aging support group locations, and on the Principal Investigator, [name] lab

webpage <http://radiology.wisc.edu/research/>. We will also release ads regarding recruitment in the media – in major newspapers such as the Wisconsin State Journal, the Milwaukee Sentinel, in the Isthmus, and through the Wisconsin Public Radio (WPR).

e) [name], the radiologist involved in clinical imaging protocols of patients, will identify patients who are suitable for study participation as they present to the UWHC, UWMF, WIMR, or Health Emotions Research Institute (HERI) for clinical imaging.

f) We have permission to contact participants who have participated in other stroke research conducted by our group ([name] 2013-1561, 2015-0469 and 2018-0398). We propose to contact these patients and ascertain interest in participating in this study.

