2. Action Research Arm Test: The Action Research Arm Test (ARAT) is designed for evaluation of upper extremity function. This test consists of sections for Grasp, Grip, Pinch and Gross Movements. Each section is scored separately and the scores added. The maximum possible total score is 57.
3. 9 Hole Peg Test: The 9-HPT is a quick and easy to administer tool for screening fine motor problems in patients. It is a timed test in which nine pegs are inserted and removed from nine holes in the pegboard with each hand.
4. Stroke Impact Scale: The Stroke Impact Scale, or SIS, was created to assess changes in impairments, activities and participation following a stroke will be used in the pre-training and post-training phase of this study. Although the SIS form allows for proxy completion, for this study, participants will be completing the SIS themselves.
5. Barthel Index: The Barthel Index measure a person's daily functioning (activities of daily living and mobility).
6. NIH Stroke scale: The National Institute of Health (NIH) stroke scale (NIHSS) is a standardized method to measure the level of impairment caused by a stroke.
7. Mini-Mental Status Examination (MMSE): The MMSE is a screening tool that provides a brief, objective measure of cognitive function.
8. Center for Epidemiologic Studies-Depression Scale (CES-D): The CES-D is a self-report scale and includes 20 items that survey mood, somatic complaints, interactions with others, and motor functioning.

9. EMG(electromyography) – is the recording of changes in skin voltage caused by contraction of the underlying muscles. This recording (EMG) will be obtained using the EMG recording equipment of the BIOPAC systems (<http://www.biopac.com/researchApplications.asp?Aid=41&Level=1>).
10. Hand grip strength: will be assessed using a dynamometer.
11. Modified Health Questionnaire: to document the general physical health and social habits of all participants.
12. Pain Scale: Patients will be asked to rate their degree of pain on a scale of 0 (no pain) to 5(in tears).[formal instructions for this scale are being included in this addendum]
13. Motor Activity Log: is a structured interview developed to assess the use of the more affected upper extremity (UE) in real-world daily activities.
14. Modified Ashworth Scale –will be used to assess muscle tone.
15. Semantic (category fluency
16. Letter or phonemic fluency (FAS)
17. Trails A and B

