25. Montreal Cognitive Assessment (MOCA) – in order to test participant for cognitive impairments [~10 minutes].
26. The Short Blessed Test, a six-item test, used as a diagnostic tool to differentiate patients with cognitive impairments from normal population will be administered. Subjects are asked to answer the items year and month, time of day, count backward 20-1, recite months backwards, and the memory phrase. This test will be administered in addition to the MMSE which also tests for cognitive impairment because the Short Blessed is known to be more sensitive to differences in levels of education and is also quicker to administer. (~ 3-4 minutes)

Pre and post intervention questionnaire – a series of questions to get a sense of the patient’s expectations, and general tiredness and motivation levels at the beginning and end of the study, and at the start of intervention each day. The questionnaire administered at the beginning of the study will ask questions regarding any allergies the patient may have and his/her experience with playing computer/video games. The post-intervention questionnaire is to get the patient’s feedback regarding their experience in the study.

B) Functional MRI scans

Participants will undergo an MRI scan without contrast lasting approximately 30 - 45 minutes at each of the five study timepoints. Participants’ pulse and respiratory rates will also be recorded in the scanner. This will require a pulse monitor (a device comfortably secured to a fingertip that uses light waves to measure pulse and blood oxygen levels) and a respiratory monitor (a belt comfortably secured around the torso that measures the depth and frequency of breaths). Neither monitor confers any risk to participants. fMRI scans will be collected while the participant is performing executed and imagined motor tasks in the scanner to examine corresponding brain activation.

Based on our ongoing study (approved under 2010-0004, 2015-0469), it is our experience that some of these patients will show contraindications for MRI (e.g., have implant or are claustrophobic etc.). We therefore propose to recruit patients who have contraindications for MRI and have them complete the behavioral assessments and intervention components of the study only.

C) Intervention

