All researchers and research staff involved in the study have completed Human Subjects and HIPAA training and will be continuously involved in data and safety monitoring. Data and safety monitoring will occur on a continuous basis. fMRI and EEG data will be reviewed by the PI, Co-I and a group of study team members on a continuous basis. All behavioral measures (e.g., ARAT, 9 holepegboard task, SIS etc.) will be reviewed by the study team within a week or two of collection.

Data Processing/Data Analysis

For Specific Aim 1:

1a) To investigate the efficacy of active FES vs. passive FES, as measured by changes in behavioral measures. A linear mixed model analysis in SPSS 22.0 will be run for each dependent measure (e.g., ARAT, SISand function) with Group (active, passive) as the between-participant factor and Time (baseline, mid, post, 1 month post) as the within-participant factor. The two baseline assessments will be averaged so as to get a stable measure of baseline performance prior to receiving intervention.

1b) To investigate the impact of BCI synchronized to FES on behavioral outcomes in the patients in the Active FES group: A post hoc analysis will be done to evaluate whether high-performers of the BCI classification task show more improvement in behavioral measures than low-performers of the BCI classification task. This will allow us to assess to what extent BCI synchronization to FES leads to improved stroke recovery. A median split of high to low performers on the BCI task will be done. We will then compare change in outcome measures of those with high performance on the BCI task (which is synchronized to FES) vs. those with low performance on the BCI task (when there is less synchronization between the BCI and FES) using unpaired t-tests. If there is a difference in the two groups then this is evidence that BCI synchronized to FES contributes to recovery, if there is no difference then this is evidence that BCI irrespective of synchronization to FES contributes to recovery.

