be used for correlation analyses between DTI and motor outcome measurements. To test whether change in FA and other diffusion values across multiple time-points correlate with change in scores on the ARAT and the SIS: The difference in each measure, example from time-point 1(T1) to T2 (i.e. change score, Δ FA or other diffusion metrics) will be calculated and separate linear regression analyses performed to see if change in diffusion values significantly correlate with change in behavioral scores. Volume of lesion affecting the white matter will be entered as covariate in the regression analysis.

Sample size considerations: Our sample size analysis is based on the primary outcome measure ARAT. For observing a minimally clinically significant difference on the ARAT of 6 points with a standard deviation of 12, from pre to post intervention, we would need a sample size of 44 participants per cell (Age By Severity with 2 levels each). This would give us 90% power to detect a significant difference. This leads to an estimated sample size of $44 \times 4 = 176$. With 10% additional recruitment to account for data loss due to participant drop-out or poor quality, we propose to recruit a total of $N = 192$ participants in this study.

Given the challenges in recruiting this population (based on our ongoing study – approved under 2010-0004, 2015-0469), we propose to also recruit patients who have contraindications for MRI and allow these patients to complete the behavioral assessments and intervention components of the study.

With the aim of meeting our sample size requirements, and also to recruit a diverse population, we had teamed up with collaborators at Milwaukee, who are also involved in stroke rehab work. Unfortunately, the original PI at Milwaukee has since moved; we have therefore decided to try and meet our goal of 144 at UW Madison and increase our efforts to recruit from the neighboring counties.

Potential Risks and Benefits

EEG Recording: The EEG electrodes are passive and only record ongoing physiological activity. Risks related to the EEG recording system include skin irritation, an unpleasant electrode gel smell, and mild discomfort associated with applying, wearing, and removing electrodes on the scalp, face, chest, and hand.

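### Do the reversed ARAT severity labels, and the risk section's wording on claustrophobia, call for a change to the plan?

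*Combined protocol and SAP*

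**What the plan says.** **Severity.** Two paragraphs under Research Design and Methods use an ARAT score of 35 to separate levels of arm impairment. The inclusion criteria admit both "mild to moderate unilateral upper extremity(UE) impairment (Action Research Arm Test; ARAT score > 35" and "severe unilateral upper extremity(UE) impairment (ARAT score <= 35". The Randomization paragraph, which balances the arms on age and severity, has "severity (severe – ARAT > 35, non-severe – ARAT <= 35". The ARAT entry under Behavioral Assessment describes a test of arm function whose section scores are added, and states that "The maximum possible total score is 57". Severity appears once more, under Sample size considerations, which asks for "44 participants per cell (Age By Severity with 2 levels each". The Aim 1 model has "Group (active, passive) as the between-participant factor and Time (baseline, mid, post, 1 month post) as the within-participant factor".

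**Claustrophobia.** The Functional MRI scans section expects that "some of these patients will show contraindications for MRI (e.g., have implant or are claustrophobic etc", and proposes to recruit such patients and "have them complete the behavioral assessments and intervention components of the study only". The note after the exclusion criteria, the end of Subject Recruitment and Sample size considerations also keep patients with MRI contraindications in the trial. The Claustrophobia entry under Potential Risks and Benefits says instead that people likely to tolerate the scanner badly are to be left out of the study.

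**The concern.** Severity is one of only two factors that steer the adaptive randomization. A definition that contradicts the eligibility section suggests that patients could be placed in the wrong stratum. If some staff worked from one paragraph and some from the other, the severity factor would become a mixture of the two groups and balance on it would weaken. Any table by severity could also carry the wrong heading.

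The claustrophobia wording bears on who gets in. Taken literally, the same patient is recruited by one section and turned away by another, in a trial that admits patients with MRI contraindications because recruitment is difficult. Staff reading different sections could apply different rules.

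**Working it through.** **1. Which severity paragraph is reversed.** The inclusion criteria pair the higher scores with the milder impairment. That fits a test of function built by adding points up to 57. The Randomization paragraph is therefore the one with the labels swapped.

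**2. Does the swap move anyone?**

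| ARAT score | Inclusion criteria | Randomization |
|---|---|---|
| 0 to 35 | severe | non-severe |
| 36 to 57 | mild to moderate | severe |

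The documents give the maximum of 57; the minimum of 0 is assumed.

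- Scores in the lower group: 35 − 0 + 1 = 36.
- Scores in the upper group: 57 − 36 + 1 = 22.
- Scores whose label is reversed: 36 + 22 = 58 of 58.
- Shift in the cut: 35 − 35 = 0 points. A score of exactly 35 falls in the lower group under both rules.
- Scores that change group: 0 of 58.

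The two rules give the same partition. Adaptive balancing depends on which patients are grouped together, not on what the group is called. Eligibility does not change either, because the inclusion criteria admit both sides of the cut.

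**3. Does the label enter an analysis?** The Aim 1 model names two factors, Group and Time; severity is neither. The Aim 2 and Aim 3 analyses do not use it. Its one other appearance is in the sample-size arithmetic, where 2 age levels × 2 severity levels = 4 cells and 4 × 44 = 176, which is the plan's own figure. Swapping the names relabels the two severe and two non-severe cells and leaves 176 as it is.

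**4. What if both labellings were used?** The stratum would then be misentered for some patients and the arms could end up less well balanced on severity. The allocation would still be random, so this costs balance and does not introduce bias. Baseline ARAT is also the first level of Time in the Aim 1 model for ARAT, so an imbalance would be visible there. The documents do not say whether staff enter a label or the score, so this case is a supposition.

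**5. Claustrophobia, side by side.**

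| Place | Patients with MRI contraindications |
|---|---|
| Note after the exclusion criteria | eligible |
| Subject Recruitment, closing paragraphs | may take part in everything but imaging |
| Functional MRI scans (names claustrophobia) | recruited, without the scan |
| Sample size considerations | recruited, to help reach the target |
| Potential Risks and Benefits, Claustrophobia | left out of the study |

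Four places agree and one differs. The one that differs belongs to a list introduced as hazards of an MRI scan, with exclusions made to reduce the risk from those hazards. A person who is not scanned does not face them. The Compensation section also calls the scan optional. In that setting, leaving someone out most naturally means leaving them out of the scan, although the words say the study.

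**6. Effect on the comparison if the literal reading were used.** Eligibility is screened by telephone before consent, and so before allocation. Turning a patient away at that stage would cost recruitment but would not affect one arm more than the other. No rate of claustrophobia is given, so the loss cannot be sized.

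**The case for a change.** The best case for acting is that both slips sit in operating rules and are cheap to correct. No reading reconciles the two severity definitions. Figure 1, to which the design paragraph refers for the randomization, is not available here, so it cannot be shown that the factor was set up by score. The screening script is not among the documents either, so it cannot be shown that claustrophobic patients are handled in one way. A literal reading would also work against the plan's own effort to widen recruitment.

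The conflict in the text stands on both counts. The step from there to a consequence does not. The Randomization paragraph itself justifies the factor by scores above or below 35 and closes by naming 35 as the cutoff, so anyone balancing on the score gets the intended strata. Nothing shows that both labellings are in use, and no analysis by severity is planned that could be misnamed. On claustrophobia, the most that can be said is that staff could read the sections differently, not that they do.

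Two neighbouring points are requests for clarification and not contradictions. The MRI entry under Potential Risks and Benefits does not say what a patient who refuses the confirmatory X-ray is barred from. The pregnancy exclusion is missing from the exclusion criteria, and carries little weight at ages 50 to 85.

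**Conclusion.** No change to the design or analysis follows. The severity labels are a clerical slip: 58 of 58 scores are renamed, 0 of 58 are regrouped, severity is in 0 of the 2 Aim 1 factors, and the 176 is unaffected. This rests on one labelling, or the score itself, being used throughout. The documents neither confirm nor contradict that, and a look at the stratum codes would settle it.

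The claustrophobia sentence is loose wording in literal conflict with the Functional MRI section and out of line with three other places. The sections should be reconciled into one statement when the text is next edited. Until then, the eligibility note and the optional status of the scan give staff a workable reading. No effect on power, type I error, sample size or the comparison of arms has been shown for either point.

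### Aim 1 enters the averaged ARAT baseline as a free level of Time; adjusting for it instead would give a small gain in precision at no cost

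*Combined protocol and SAP*

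**What the plan says.** Item 1a, under Data Processing/Data Analysis for Specific Aim 1, fits a linear mixed model to each behavioral measure "with Group (active, passive) as the between-participant factor and Time (baseline, mid, post, 1 month post) as the within-participant factor". It adds: "The two baseline assessments will be averaged so as to get a stable measure of baseline performance prior to receiving intervention". No covariate is listed, so baseline ARAT is one of the four outcome levels and its mean may differ freely between groups.

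Item 1a does not name the term to be tested. The aim is to assess efficacy "as measured by changes in behavioral measures", and the hypothesis under Specific Aims is that "improvements in motor function will be significantly greater using the active FES therapy than the passive FES therapy". Both point to Group x Time, which I take as the test here. Sample size considerations names ARAT as the primary outcome.

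**The concern.** With baseline as an unconstrained Time level, the Group x Time contrast at a later visit equals, with complete data, the difference between groups in mean change from baseline. A change score subtracts the whole baseline value, which amounts to fixing the slope of follow-up on baseline at 1. Baseline is measured with visit-to-visit variation even after averaging, so the best-fitting slope is below 1 and the change score carries avoidable noise. Randomization makes the expected baseline means equal, so adjusting for baseline estimates the same group effect with a smaller standard error.

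At stake is a little power on the primary outcome. The plan already reports difficulty in recruiting and the loss of a collaborating site, and the data needed are already collected.

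**Working it through.** **The plan's own figure.** Sample size considerations uses 6 points, SD 12, 90% power and 44 per cell. A paired t-test of pre-to-post change, two-sided 5%, gives power 0.9000 at n = 44, so the figure reproduces as a within-cell change. As a two-group comparison the same inputs need 85 to 86 per arm (0.8999 and 0.9032); 44 per arm gives 0.640. The plan therefore states no power for active versus passive, and the powers below are illustrations.

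**Inputs.**
- From the documents: 72 per arm; 10% loss, so 72 x 0.9 = 64.8, about 65 per arm; ARAT range 0 to 57; two baselines averaged.
- Assumed: two-sided 5%; a 6-point difference between groups; SD 12 as the SD of change from the averaged baseline; compound symmetry across visits; single-visit ARAT SD (S) of 15, 20 or 25.

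**Formulas.** Write S² = sb + se, with sb the between-participant and se the visit-to-visit variance.
- Variance of the averaged baseline: sb + se/2
- Variance of change: se + se/2 = 1.5 se
- Variance of the later value adjusted for baseline: S² − sb²/(sb + se/2)

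From 1.5 se = 144, se = 96.

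| S | sb | Adjusted variance | Ratio to 144 |
|---|---|---|---|
| 15 | 129 | 225 − 129²/177 = 130.98 | 0.910 |
| 20 | 304 | 400 − 304²/352 = 137.45 | 0.955 |
| 25 | 529 | 625 − 529²/577 = 140.01 | 0.972 |

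**Power, post-visit contrast (noncentral t).**

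| Per arm | As planned | S = 15 | S = 20 | S = 25 |
|---|---|---|---|---|
| 72 | 84.6% | 87.8% | 86.2% | 85.6% |
| 65 | 80.8% | 84.3% | 82.5% | 81.8% |

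In participants, 72/0.910 = 79.1, 72/0.955 = 75.4 and 72/0.972 = 74.1, so adjustment is worth about 2 to 7 per arm.

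**Other reading of SD 12.** If it is the SD of change between two single visits, 2 se = 144 and se = 72. Change from the averaged baseline then has variance 108, and the adjusted variances are 101.14, 104.44 and 105.80. Power at 72 per arm goes from 93.1% to 94.5%, 93.8% and 93.5%, a gain of about 0.5 to 1.4 points.

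**Joint test over mid, post and 1 month (3 df, multivariate F, 72 per arm, se = 96).** The covariance of the three changes is se·I + (se/2)·J, where I is the identity and J the all-ones matrix. After adjustment, se/2 is replaced by sb − sb²/(sb + se/2), which is smaller. For a uniform 6-point effect the noncentrality is (72/2) x 3 x 36/(96 + 3 x 48) = 16.2 as planned. With S = 15 it is (72/2) x 3 x 36/(96 + 3 x 34.98) = 19.3 adjusted.

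| Effect at mid, post, 1 month | As planned | Adjusted, S = 25 to 15 |
|---|---|---|
| 6, 6, 6 | 93.0% | 94.2%-96.6% |
| 3, 6, 6 | 87.4% | 88.9%-92.2% |
| 0, 6, 0 | 78.3% | 78.7%-79.8% |

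**Does a plain age term do the same?** No. With S = 15 and 72 per arm, the standard error of the post-minus-baseline Group contrast is √(144 x 2/72) = 2.000, with or without an age main effect. Constraining the baseline means to be equal gives √(130.98 x 2/72) = 1.907.

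**Bias.** In simulations with a true 6-point effect, the mean estimate was 6.0 (to one decimal) both with and without baseline adjustment.

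**The case against.** Group and Time with baseline as a level is a conventional and valid analysis, and averaging two baselines already captures part of the gain. The size of the remainder rests on inputs that the documents do not give. The trial enrols patients on both sides of ARAT 35 on a 57-point scale, so the single-visit SD could be large; at S = 25 the gain at 72 per arm is only about 1.0 point, or 0.5 on the other reading of SD 12. All of this stands. It limits the size of the point but does not reverse its direction.

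Three stronger readings are tempting and are not supported.

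- A reader might infer that the loss comes from leaving out the allocation factors, since "Adaptive randomization in our study will be done based on age and severity of UE impairment". As main effects, age and severity leave the Group x Time contrast unchanged; they can matter only if crossed with Time or placed in a model of the post-baseline values. Severity is ARAT cut in two, so it adds little once baseline ARAT is in. The rationale for age, that "Advancing age has a major negative impact on stroke morbidity, mortality", concerns survival and discharge rather than change in ARAT; only the ARAT cut-off is tied to recovery ("There is some evidence that patients with ARAT scores above or below 35 show clear differences in recovery").
- A reader might infer bias or inflated false positives. Neither follows: the planned contrast estimates the same effect, only with more noise.
- A reader might infer that Aim 1 should be decided at the post visit alone. That is not free. Under the same assumptions, for a uniform 6-point effect, the unadjusted joint test has 93.0% power against 85.6%-87.8% for the adjusted post-visit contrast. Baseline adjustment helps either choice and should not be bundled with it.

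**Conclusion.** The point holds as a small improvement in precision, with no bias and no false-positive risk in the plan as written. Under the stated assumptions the gain at the post visit is about 1.0 to 3.2 power points at 72 per arm and 1.0 to 3.5 at 65 per arm. It is about 0.5 to 1.4 points at 72 per arm if SD 12 refers to single-visit change. The direction follows whenever the between-visit correlation is below 1 under compound symmetry; the size depends on the assumed ARAT SD, correlation pattern and 6-point between-group effect. The point presumes that Group x Time is the test. Naming that term in item 1a is a separate matter of specification.

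**What to change.** In item 1a, model the mid, post and 1-month ARAT values with Group, Time, Group x Time, averaged baseline ARAT and baseline x Time, using an unstructured covariance. Equivalently, keep baseline as a Time level and constrain its mean to be equal across groups. The covariance should again be unstructured, because an average of two visits varies less than a single visit. Treat the other behavioral measures in the same way, each with its own baseline.

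Age group crossed with Time may be added, but helps only if age predicts ARAT change. A severity term is not needed. If one is wanted, the documents must first be reconciled: the inclusion criteria attach severe impairment to ARAT of 35 or below, while Randomization has "severity (severe – ARAT > 35, non-severe – ARAT <= 35".

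The cost is a change of wording before analysis. Both baseline assessments are already planned for every participant, and no visit, measure or sample size changes.

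### Aim 1b splits BCI performance at the median and compares change without baseline covariates; this loses information and leaves the comparison open to confounding by severity

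*Combined protocol and SAP*

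**What the plan says.** The analysis is item 1b under Specific Aim 1 in Data Processing/Data Analysis. Its stated purpose is "To investigate the impact of BCI synchronized to FES on behavioral outcomes in the patients in the Active FES group", and it is described as post hoc. The method has two steps. First, "A median split of high to low performers on the BCI task will be done". Then "We will then compare change in outcome measures of those with high performance on the BCI task" with the low performers, "using unpaired t-tests". No covariate is named.

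The plan attaches a mechanistic conclusion to a positive result: "If there is a difference in the two groups then this is evidence that BCI synchronized to FES contributes to recovery".

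The Randomization section plans 72 patients in the active arm and stratifies on age and ARAT severity. It gives as its reason for the ARAT cut-off: "There is some evidence that patients with ARAT scores above or below 35 show clear differences in recovery". Neither age nor severity appears in any analysis model. The Aim 1a model contains Group and Time only. The one covariate named anywhere is white-matter lesion volume, in the Aim 3 regressions.

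**The concern.** There are two separate problems.

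**Form of the exposure.** Item 1b asks about extent, which is a question about a gradient. A high/low contrast does not estimate a gradient. It treats patients just either side of the median as opposites and patients far apart within one half as identical. The plan keeps comparable measures continuous elsewhere: change in LI is correlated with behavioral change in Aim 2, and change in diffusion values enters a regression in Aim 3.

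**Missing baseline terms.** Randomization balances the two arms. It does not balance high and low performers within one arm. The active arm includes severe and non-severe patients by design, and the protocol cites some evidence that recovery differs between them. Taking change scores subtracts the baseline level but does not adjust for baseline as a predictor of change. If more or less severe patients also perform differently on the BCI task, part of any high/low difference belongs to severity.

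At stake is the plan's only within-arm exposure-response analysis. It could miss a real gradient, or credit synchronization with a difference that arises from baseline condition.

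**Working it through.** **The plan's own figure.** The documents give no power for 1b. The Sample size considerations give 44 per cell for 6 ARAT points, SD 12 and 90% power. A paired t-test on pre-post change (d = 6/12 = 0.5, two-sided 5% assumed because no alpha is stated) gives n = 44 with power 0.900, so the figure reproduces. It is a pre-post number and does not cover a comparison of two halves of one arm. For 36 against 36 at SD 12, the standard error is 12 × √(2/36) = 2.83. Power for 6 points is then Φ(6/2.83 − 1.96) = 56%, and the difference detectable with 80% power is (1.960 + 0.842) × 2.83 = 7.9 points.

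**Information lost by the split.** The share retained is the squared correlation between the score and its median indicator. For a normal score this is 2/π = 0.637, a loss of 36.3%, so 72 patients are worth 72 × 0.637 ≈ 46 analysed continuously. The documents give no distribution for BCI performance. Other shapes tried (one million draws each) gave these losses:

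| Score distribution | Loss |
|---|---|
| Bimodal | 23% |
| Uniform | 25% |
| Beta(2,2) | 30% |
| Beta(5,2) | 35% |
| Lognormal, sigma 0.5 | 48% |
| Exponential | 52% |

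**Power.** Inputs: n = 72 (Randomization), or 72 × 0.9 ≈ 65 after the plan's 10% allowance. Two-sided 5% and the true correlations r are assumptions. The split reduces r to √(2/π) × r = 0.798r. Power ≈ Φ(atanh(r) × √(n − 3) − 1.96).

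For r = 0.30 and n = 72:
- Continuous: atanh(0.30) × √69 = 0.3095 × 8.307 = 2.571, so power = Φ(0.611) = 73%.
- Split: atanh(0.239) × √69 = 0.244 × 8.307 = 2.027, so power = Φ(0.067) = 53%.

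| True r | n = 72 continuous | n = 72 split | n = 65 continuous | n = 65 split |
|---|---|---|---|---|
| 0.30 | 73% | 53% | 68% | 48% |
| 0.35 | 86% | 66% | 82% | 62% |
| 0.40 | 94% | 78% | 92% | 74% |

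Simulation at n = 72 (20,000 runs per setting) agrees: 73.5% against 53.0% at r = 0.30, and 94.5% against 79.9% at r = 0.40.

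**Confounding.** Set the true BCI effect to zero. Let severity, taken as a continuous normal variable, correlate a with BCI score and b with ARAT change. The expected spurious difference between halves is 2 × √(2/π) × a × b × SD = 19.15ab points at SD 12. For a = b = 0.3 this is 1.7 points. Simulation at n = 72 gave:

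| a = b | Spurious difference (ARAT points) | Type I error, split t-test | Type I error, continuous score adjusted for severity |
|---|---|---|---|
| 0.2 | 0.8 | 5.9% | 4.9% |
| 0.3 | 1.7 | 9.2% | 5.1% |
| 0.4 | 3.0 | 18.7% | 4.7% |
| 0.5 | 4.7 | 38.2% | 5.0% |

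With a = 0, the split test rejected 4.9% to 5.2% of the time whatever the value of b. For scale, the plan's clinically significant difference is 6 points. The values of a and b are assumptions.

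**The case against.** Much of the case for leaving 1b alone is sound. It is labelled post hoc, no power is claimed for it, and nothing here touches the randomised comparison in Aim 1a. That limits the importance of the point. But the analysis is written into the plan with a mechanistic conclusion attached, and a better one costs a few sentences.

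A reader might infer more than the documents support, in four ways:

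- **That severity is shown to pass for a BCI effect.** This needs severity to be linked both to recovery and to BCI performance. The protocol gives hedged support for the first and reports nothing on the second. Confounding is therefore a risk the analysis cannot rule out, of unknown direction and size.
- **That the split always costs about a third.** That figure belongs to a roughly normal score with a linear effect; hence the range of 23% to 52%.
- **That a cut-off taken from the sample inflates type I error.** It does not. The median is a rule fixed in advance and blind to outcome, unlike a cut-point chosen to maximise a difference. The cost is efficiency.
- **That adjustment makes 1b causal.** Lesion and cognition would remain uncontrolled, and performance averaged over training may itself be a consequence of recovery.

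It is also fair to say that linear regression has its own weak points: linearity is assumed, and ARAT is capped at 57 while patients above 35 enter with no upper limit. These are reasons to check the model. A median split imposes a cruder step function and does nothing about the ceiling.

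**Conclusion.** The point stands as a recommended improvement to a secondary, exploratory analysis.

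The efficiency loss follows from the split itself. Its size depends on the score distribution and on linearity. The power figures also rest on 72 patients, two-sided 5% and assumed correlations of 0.30 to 0.40.

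The confounding is conditional. The false-positive rate ranges from the nominal 5%, if severity and BCI performance are unrelated, to 38% if severity correlates 0.5 with both performance and change. The documents do not show where in that range this trial lies.

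**What to change.** Replace the median split and t-tests in 1b with wording to this effect: for each behavioral outcome, ARAT first, fit within the active FES arm a linear regression of the post-intervention score on BCI classification performance as a continuous variable, adjusted for the averaged baseline value of that outcome, baseline ARAT and age. For ARAT itself the first two adjustments coincide. Report the slope with its 95% CI, label it exploratory and observational, and keep the high/low split for display only.

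The wording should also define the performance measure, its unit and how it is summarised over sessions, because the documents do not. Check residuals for non-linearity and for a ceiling near 57 on ARAT.

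Using ARAT as a number also avoids relying on the severity labels. These run in opposite directions in the inclusion criteria (35 or below is severe) and the Randomization section (above 35 is severe), and the two passages must be reconciled in any case.

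The cost is a few sentences of analysis-plan text and no new data, since baseline scores and age are already collected.
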